11.3 Schedule of study procedures of the pilot intervention trial

	Visit 3 (14 ± 2 days after visit 2)	Visit 4 (4 weeks ± 1 week after visit 2)	Visit 5 (2years ± 4 weeks after Visit 4)
Application of continuous glucose monitoring	X		
Concomitant medication		X	X
Vital signs		X	X
Physical examination		X	X
Blood sampling		X	X
Oral glucose tolerance test (OGTT)		X	
Continuous Glucose monitoring (CGM)		X	
Endothelial function (EndoPat 2000)		X	
Buccal mucosa sampling		X	
Saliva sampling		X	
Faeces sampling		X	
Resting energy expenditure (REE)		X	
Questionnaires (FFQ, Physical Activity)		X	X
Bioelectrical impedance analysis (BIA)		X	
Flow mediated dilatation (FMD)		X	

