4. SYNOPSIS

Study title	InterFast
Study design	Cohort study with an embedded randomized controlled pilot trial
Study participants	Healthy subjects and subjects who do already practice Alternate Day Fasting
Number of participants	90 (30 Participants in Alternate Day Fasting group and 60 participants in the control group). Those participants in the control group will be asked to participate in a short randomized controlled trial, where they will be either allocated to an Alternative Day Fasting group or another control visit.
Planned duration	18 months
Primary objective	The primary objective is to elucidate in which extent alternate day fasting influences human physiology in healthy individuals in both, the short and long term. Data of the pilot RCT will help to design a larger trial investigating Alternate Day Fasting in various groups of interest.
Secondary objectives	The secondary objective of this study is to define novel molecular markers of aging and age-related diseases.

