10.5 Withdrawal / Drop out of subjects

Each subject has the right to withdraw from the study at any time without prejudice or compromise to future care.

The investigator may discontinue or withdraw the subjects under the following circumstances:

- Significant protocol deviation
- Significant non-compliance with treatment regime or study procedures
- An adverse event that requires discontinuation of the study medication or results in inability to continue to comply with study procedures. If a subject is withdrawn due to an adverse event, the investigator will arrange for follow-up visits or telephone calls until the adverse event has resolved or stabilised.
- Consent withdrawn
- Lost to follow up
- Any other situation that may, in the opinion of the investigator, make it unsafe or inappropriate for the subject to continue in the trial

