11.2 Visit Schedule for the cohort study

Visit 1

- Sufficient time will be provided and subjects will be encouraged to discuss all queries with the research team
- Informed consent for the study will be obtained by an investigator
- Biobank informed consent will be obtained by an investigator
- Check inclusion and exclusion criteria

- Demographics will be obtained: date of birth, gender, race, smoking status, alcohol consumption
- Weight
- Height
- Waist-Hip Ratio
- Medical history and standardized questionnaire on fertility outcomes
- Concomitant medication
- Vital signs: resting pulse and blood pressure
- Blood sampling
- ECG
- Food Frequency Questionnaire and Ferriman-Galway Score/Hamilton-Norwood Scheme
- Baseline blood tests (fasting): Full blood cell count, renal function tests, liver function tests,
- Pregnancy test in female woman of childbearing age
- Oral glucose tolerance test (OGTT)
- Application of the 24h blood pressure device
- Application of continuous glucose monitoring
- Application of accelerometer (Movisens®)

Visit 2 (9 ± 4 days after visit 1)

- Vital signs, Weight
- Physical examination
- Concomitant medication review
- Resting energy expenditure (REE)
- Measurement of endothelial function (EndoPAT 2000)
- Flow mediated dilatation (FMD)
- Blood sampling
- Oral glucose tolerance test (OGTT)
- IMT measurement
- Retinal vessel analyser
- Hand Grip Test
- Pulse wave analysis
- Echocardiography
- Collection and analysis of 24h blood pressure monitor
- Collection and analysis of accelerometer

- Removal of continuous glucose monitoring
- Dual-energy X-ray absorptiometry (DXA) and hand grip test
- Collection of sputum and faeces samples
- Buccal mucosa sampling
- Informed consent for RCT (healthy control group willing to participate in the RCT)
- Bioelectrical impedance analysis (BIA)
- Dry eye assessment (optional)

Visit 3 (2 weeks before visit 4) → only those subjects participating in the pilot RCT

- Application of continuous glucose monitoring

Visit 4 (4 weeks ± 1 week after visit 2) → only those subjects participating in the pilot RCT

- Vital signs, Weight
- Physical examination
- Concomitant medication review
- Resting energy expenditure (REE)
- Measurement of endothelial function (EndoPAT 2000)
- Flow mediated dilatation (FMD)
- Blood sampling
- Food Frequency Questionnaire
- Oral glucose tolerance test (OGTT)
- Removal of continuous glucose monitoring
- Collection of sputum and faeces samples
- Buccal mucosa sampling

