14. ETHICS

The Investigator will ensure that this study is conducted in accordance with the principles of the Declaration of Helsinki, GCP-ICH and according to the protocol and the requirements of the concerned regulatory authorities. The measurements taken are either non-invasive or minimally invasive (blood sampling). Therefore we consider this trial as low risk for participants.

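### Section 10.5 acts on adverse events, but no pilot visit asks about them, so harms of the randomised fasting regimen would be captured only incidentally

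*Protocol*

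**What the plan says.** Protocol section 10.5 lists among the grounds for withdrawal: "An adverse event that requires discontinuation of the study medication or results in inability to continue to comply with study procedures". It adds a duty of follow-up: "If a subject is withdrawn due to an adverse event, the investigator will arrange for follow-up visits or telephone calls", continuing until the event resolves or stabilises.

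The pilot's visits are itemised twice, as lists in 11.2 and as a table under "11.3 Schedule of study procedures of the pilot intervention trial". The table places the two visits after RCT consent at "Visit 3 (14 ± 2 days after visit 2") and "Visit 4 (4 weeks ± 1 week after visit 2"). Visit 5 follows two years after Visit 4. The single item at Visit 3, in both sections, is "Application of continuous glucose monitoring". Visits 4 and 5 carry longer lists, but neither includes a question about adverse events or tolerability.

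The synopsis gives the pilot's purpose: "Data of the pilot RCT will help to design a larger trial investigating Alternate Day Fasting in various groups of interest".

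**The concern.** A rule that acts on adverse events needs a way of finding them. The schedules list procedures down to stool and saliva samples, so an absent item is probably not just shorthand. As written, an adverse event reaches the investigator if the participant volunteers it or if it shows up in an examination, a blood result or a medication change.

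Two things are at stake. First, symptoms that leave no trace in those checks, such as feeling unwell on fast days, may go unrecorded during the period when someone could respond to them. Second, the two arms may not be comparable on what is recorded. Participants know whether they are fasting, and spontaneous reporting can depend on that knowledge. The protocol gives no figure for the size or direction of such a difference, so this is general reasoning and not a measured bias. Tolerability relative to control is nonetheless basic information for planning a larger trial, and the pilot could collect it at visits that already take place.

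**Working it through.** **Step 1. Search for an adverse event item.**

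| Place in the protocol | What it holds on harms |
|---|---|
| 10.5 | Adverse event as a withdrawal ground; follow-up only of those withdrawn for one |
| 9.3 (CRF content) | Demographics, history, medications, diet; adverse events not named |
| 11.2 and 11.3, Visit 3 | Sensor application only |
| 11.2 and 11.3, Visit 4 | Vital signs, examination, medication review, blood, OGTT, glucose monitoring, questionnaires and others; weight in 11.2. No adverse event item |
| 11.2 and 11.3, Visit 5 | Vital signs, examination, medication review, blood, questionnaires; weight in 11.2. No adverse event item |
| 12.8 and 12.22 (questionnaires) | Food intake, fertility and hair scores; physical activity. No general symptom enquiry |
| 12.1 | Routine safety laboratory panel with the OGTT, hence at Visit 4 |
| 11.4 | Physician grades laboratory results; the only stated action is an eligibility review |
| 8.3 and 8.4 | No readable outcome on harms or tolerability (one item in 8.3 is a figure not shown) |

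**Step 2. Contacts between consent and assessment.** By 11.3, Visit 3 falls 14 − 2 = 12 to 14 + 2 = 16 days after Visit 2, and Visit 4 falls 3 to 5 weeks after Visit 2. Section 11.2 instead counts Visit 3 back two weeks from Visit 4. Either way there is one scheduled contact in between, with one procedure. The protocol does not date the start or end of fasting. That this interval is the time on the regimen is inferred from consent at Visit 2 and assessment at Visit 4.

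**Step 3. Pilot size.** Section 12.26 expects 40% acceptance and about 10 per group.

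- With the 50 controls of that section: 0.40 × 50 / 2 = 10, which reproduces the stated figure.
- With the 60 controls of the synopsis: 0.40 × 60 / 2 = 12.

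**Step 4. What complete collection could show.** The event rates p below are assumptions; the protocol gives none.

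- One-sided 95% upper limit with zero events, 1 − 0.05^(1/n): n = 10 gives 0.259; n = 12 gives 0.221.
- Chance of seeing at least one event, 1 − (1 − p)^n:

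| True rate p | n = 10 | n = 12 |
|---|---|---|
| 5% | 0.401 | 0.460 |
| 10% | 0.651 | 0.718 |
| 20% | 0.893 | 0.931 |

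These figures do not measure the gap. They would be the same after the fix, and they show how far a pilot of this size can go once events are asked about.

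**The case against.** The strongest reply is that the pilot already collects a good deal on safety. Visit 4 closes the interval with vital signs, weight, examination, medication review and a safety laboratory panel graded by a physician. A glucose sensor is worn from Visit 3 to Visit 4. Both arms follow the same visits, and withdrawals for adverse events or non-compliance can be counted. This stands. A reader might infer that the pilot cannot report harms or tolerability at all, and the protocol does not support that. What is missing is narrower: a systematic question put to both arms.

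Three other inferences also go too far.

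- Section 14 says "The measurements taken are either non-invasive or minimally invasive (blood sampling). Therefore we consider this trial as low risk for participants". A reader might take this as the reason for the omission and as setting the monitoring frequency in section 13. Section 14 does not mention adverse event collection. Section 13 calls for a risk-based approach without referring to that statement, and it concerns protocol compliance and accuracy against source documents. No change to either section is needed for this point.
- The two years between Visits 4 and 5 might be read as two years of unmonitored fasting. Nothing says that the allocated regimen continues after Visit 4.
- The cohort visits also lack an adverse event item, but they precede allocation and compare existing habits, so the point does not depend on them.

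It can also be said that the synopsis promises only help with a larger trial, not a tolerability rate, and that one primary outcome item is unreadable. Both are true. Neither supplies the missing enquiry, because the schedules are fully readable.

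**Conclusion.** The point holds in a limited form. Section 10.5 depends on adverse events being known, while 11.2 and 11.3 contain no enquiry about them at any pilot visit, and the one contact between consent and assessment only fits a sensor. Run as written, the pilot would record harms of the fasting regimen incidentally, through Visit 4 checks, withdrawals and volunteered reports, and not comparably by arm.

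No power or sample size figure decides this; it is a gap in what is collected. It belongs in the protocol, because an analysis plan cannot recover data that no visit gathers. The conclusion rests on the readable text and on the inferred timing of the regimen between Visits 2 and 4. It is worth correcting because the remedy is cheap, not because the trial's main comparisons are threatened.

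A smaller inconsistency in the same rule needs attention: 10.5 speaks of discontinuing a study medication, whereas the randomised intervention is a diet.

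**What to change.** Reconcile 10.5 with 11.2 and 11.3:

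- Add the same open adverse event question, worded identically for both randomised arms, at Visits 3, 4 and 5 in both sections.
- Add a CRF field for the answer.
- Name adverse events and withdrawals by arm as a descriptive pilot outcome in 8.4.
- Reconcile the study medication wording in 10.5 with the dietary intervention.

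The cost is slightly longer visits that already take place, one CRF field and one descriptive table. The table should carry exact limits, so that an absence of events among 10 to 12 participants per arm is not read as evidence of safety.

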11.4 Laboratory results

All laboratory results will be reviewed and the reports signed by the study physician who will record whether it is normal, abnormal but not clinically significant, or abnormal and clinically significant. In the latter case, the eligibility of the subject will be reviewed.

12. METHODS

12.1 Oral glucose tolerance test (OGTT)

Various insulin sensitivity indices derived from a frequently sampled, extended oral glucose tolerance test (OGTT) will be calculated accounting for the various weighting of hepatic and peripheral insulin sensitivity expressed by the different indices. Insulin, C-peptide and glucose will be measured before and 15, 30, 60 and 120 minutes after ingestion of 75g glucose ([®]Glucoral 75 citron, Germania Pharmazeutika, Vienna). In addition, lipid-parameters (total cholesterol, triglycerides, HDL, LDL, free fatty acids) and a routine safety lab will be measured. The OGTT will be performed after an overnight fast (apart from water). A standard gauge cannula will be placed into a subcutaneous vein for blood sampling. In order to prevent blood clotting in the cannula and to keep the cannula working it will be occasionally flushed with sterile normal saline. A pre-meal blood sample will be taken (-5 mins) and then all subjects will be asked to drink the sugar solution over a period of 2-4 mins (time 0 min). During the OGTT further blood samples will be taken at 15, 30, 60, and 120 minutes. The blood at each time point will be placed into a fluoride oxalate tube (1ml) for plasma glucose and into a serum tube for analyses of insulin and c-peptide.

The insulin sensitivity index will be calculated from the OGTT according to four different equations: the

Matsuda-Index (IS_{OGTT}): $IS_{OGTT} = \frac{10000}{\sqrt{(glucose_0 * insulin_0) * (mean\ glucose * mean\ insulin)}}$,¹⁴ the HOMA-IR

(Homeostasis Model Assessment for Insulin Resistance): $HOMA - IR = \frac{FPG(\text{mmol/l}) * FSI(U/l)}{22.5}$ ¹⁵ and the

$QUICKI = \frac{1}{\log(insulin_0) + \log(glucose_0)}$ ¹⁶. The last equation was proposed by Stumvoll et al. (insulin

sensitivity index ISI): $ISI = 0.222 - 0.00333 * BMI - 0.0000779 * Ins_{120} - 0.000422 * age$ ¹⁷.

Beta-cell function will be estimated in the fasting state with $HOMA - \beta = \frac{20 * Insulin_0}{Glucose_0 - 3.5}$ ¹⁵ and during

the OGTT with the Stumvoll-Index: $1st\ phase = 1283 + 1.829 * Ins_{30} - 138.7 * Glc_{30} + 3.772 * Ins_0$ plus $2nd\ phase = 286 + 0.416 * Ins_{30} - 25.94 * Gluc_{30} + 0.926 * Ins_0$ ¹⁷ and the ratio

of the incremental insulin to glucose response over the first 30min during the OGTT $\frac{\Delta Insulin(30)}{\Delta Glucose(30)}$.

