5. BACKGROUND AND RATIONALE

Intermittent fasting is a dietary regimen defined by alternating fasting and “feeding” cycles. In addition to caloric restriction (a dietary regimen limited to a daily food intake lower than one’s daily caloric needs) only, intermittent fasting seems to activate cell autophagy (cellular “recycling” program) which potentially increases cellular stress resistance and removes accumulated molecules that are potentially toxic¹⁻³. In fact, mice maintained on intermittent fasting without decreased overall food intake show effects on body weight reduction that equal and in some cases even exceed those of calorie restriction^{4, 5}. However, additionally, intermittent fasting combined with even a high-fat diet in the feeding periods protects mice from obesity, hyperinsulinemia, hepatic steatosis, and inflammation compared to controls that are fed an *ad libitum* high-fat diet despite the same calorie intake⁶, making this intermittent fasting regimen a promising approach to reduce morbidity and mortality in various species.

The best described and most widely practiced version of intermittent fasting is the “alternate day diet” or “alternate day fasting” (ADF). In animal models, ADF consists of an *ad libitum* “feed day” alternated with a 100% restriction “fast day”. However in humans, this is often modified to allow a small amount of food consumption on the “fast day” (e.g. 25% of the individual’s energy needs). Findings from recent modified ADF studies showed 4-8% reduction in body weight after 8-12 weeks⁷⁻¹⁰. This reduction in body weight is usually escorted by reductions in triglycerides^{8, 10, 11}, low density lipoprotein (LDL) cholesterol^{8, 10, 11}, systolic blood pressure¹⁰, insulin resistance⁷ and increases in LDL particle size^{7, 12, 13}.

However, knowledge about the molecular effects of the alternate day diet on human metabolism or autophagy is still scarce since detailed analyses of molecular and metabolic parameters remain unexplored, especially in healthy individuals. The overarching aim of this research project is to elucidate in which extent alternate day fasting (and thereby intermittent fasting) influences human physiology in healthy individuals in both short and long term. The secondary objective of this study is to define novel molecular markers of aging and age-related diseases.

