11. STUDY PROCEDURES

11.1 Schedule of study procedures of the cohort study

	Visit 1	Visit 2 (9 ± 4 days after visit 1)
Informed Consent	X	
Inclusion/exclusion criteria	X	
Demography, medical history	X	

Concomitant medication	X	X
Vital signs	X	X
Physical examination	X	
Blood sampling (FMD)	X	X
Dual-energy X-ray absorptiometry (DXA)		X
Oral glucose tolerance test (OGTT)	X	X (ADF group only)
Electrocardiography (ECG)	X	
Questionnaires (FFQ, Physical Activity)		X
Retinal vessels analyser		X
Continuous Glucose monitoring (CGM)	X	
Hand-Grip Test		X
Accelerometer (Movisens®)	X	
Endothelial function (EndoPat 2000)		X
Intima media thickness (IMT)		X
Pulse wave analysis		X
Buccal mucosa sampling	X	
24h blood pressure measurement	X	
Sputum sampling	X	
Faeces sampling	X	
Echocardiography	X	
Resting energy expenditure (REE)		X
Bioelectrical impedance analysis (BIA)		X
Dry eye assessment (optional)		X
Flow mediated dilatation (FMD)		X

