12.2 Endothelial function

Endo-PAT 2000 (Itamar Medical Ltd., Caesarea, Israel) will be used to measure endothelium-dependent vaso-reactivity as previously described¹⁸. In brief, before measurements, the subjects will be in supine position for a minimum of 10 minutes, in a quiet, temperature-controlled room with dimmed lights.

Probes will be placed on both index fingers and pulse wave amplitudes will be detected and recorded during the study. After a five-minute baseline measurement, arterial flow will be occluded using a cuff on the non-dominant arm. The cuff will be inflated to 60 mmHg above systolic pressure. After five minutes of occlusion, the cuff will be rapidly deflated to allow reactive hyperemia. Pulse wave amplitudes will be recorded again for at least five minutes. The ratio of the peripheral arterial tone (PAT) signal after cuff release compared with baseline will be calculated through a computer algorithm automatically normalizing for baseline signal and indexed to the contra lateral arm. The calculated ratio represents the reactive hyperemia index (RHI) ¹⁹.

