12.9 Non-invasive 24h ambulatory blood pressure monitoring

Subjects wear the blood pressure device for a single 24-hours period. During this time, the device is programmed to inflate and record blood pressure at pre-specified intervals (usually every 15min during daytime hours and every 30 minutes during night-time hours), which provides approximately 50-75 blood pressure recordings during the 24-hours period. Study participants are asked to keep an activity log throughout the 24-hour period so activities can be mapped onto the blood pressure recordings. The process for educating subjects about the blood pressure device and setting up the test takes

approximately 10 minutes. Patients should undergo testing on a regular workday. They should be educated about the process of monitoring and the importance of maintaining an activity log.

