12.10 Resting energy expenditure (REE)

The resting energy expenditure (REE) is a component of energy expenditure that is measured by indirect calorimetry (IC). Subjects must at least 30-minute rest after at least 8 hours of sleep and after at least 3 hour fasting. During measurement, subject must be kept fully awake, lied down quietly, completely relaxed and breathing normally. The measurements took place for at least 30 minutes and were performed in standard neutral hospital room temperature. A breath mask will be placed over the head of the subject. Oxygen consumption and carbon dioxide production will be measured and energy expenditure will be calculated by the Weir formula ²⁵.

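### The protocol neither fixes nor records whether ADF participants are measured after a fast day or a feed day, so an acute fast can enter the group difference for the acutely sensitive primary outcomes

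*Protocol*

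**What the plan says.** Protocol section 12.1 derives all four insulin sensitivity indices from the OGTT and sets one nutritional condition: "The OGTT will be performed after an overnight fast (apart from water"). Section 12.10 says for resting energy expenditure (REE): "Subjects must at least 30-minute rest after at least 8 hours of sleep and after at least 3 hour fasting". Section 12.9 says of blood pressure: "Subjects wear the blood pressure device for a single 24-hours period", and adds: "Patients should undergo testing on a regular workday". For EndoPAT, section 12.2 asks that "the subjects will be in supine position for a minimum of 10 minutes, in a quiet, temperature-controlled room with dimmed lights" and says nothing about food. Sections 12.12 (pulse wave analysis) and 12.25 (FMD) also set no nutritional condition.

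The timing rules are "Visit 2 (9 ± 4 days after visit 1") and, for the pilot RCT, "Visit 4 (4 weeks ± 1 week after visit 2"). Visit 1 is not tied to any day of the ADF cycle.

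The table in section 11.1 schedules an OGTT at Visit 1 for everyone and a second one at Visit 2 for the ADF group only. Section 11.2 lists the Visit 2 OGTT without that restriction.

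Fast days and feed days are mentioned only in section 5. Section 6 assigns long-term effects to cohort members who already practise ADF, and short-term effects to those randomized to it. Insulin sensitivity is a primary outcome in both parts (8.1, 8.3). REE, RHI, augmentation index, 24 h blood pressure and appetite hormones are primary in the cohort. Change in endothelial function is primary in the RCT, where EndoPAT and FMD are both scheduled.

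**The concern.** The exposure under study is itself a cycle of fasting and eating. An overnight fast standardizes the controls, but it does not by itself standardize ADF participants. The morning after a feed day and the morning after a fast day can both satisfy the rule, and the two states may differ in recent intake.

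If some or all ADF participants attend after a fast day, the ADF-minus-control difference contains a component from one recent fast that no control has. In the cohort this is added to the effect of habitual ADF. At Visit 4 of the RCT it is added to the effect of about four weeks of ADF, and the baseline measurement has no such component. An observed difference in insulin sensitivity, REE or vascular function could then not be attributed to the regimen rather than to the day before the visit. The phase is decided when the visit is booked, so later analysis can adjust for it only if it was recorded.

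**Working it through.** **1. Is the phase fixed anywhere?** Setting the rules side by side:

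| Measurement | Section | Nutritional condition | Fast/feed day fixed? |
|---|---|---|---|
| OGTT indices | 12.1 | overnight fast | no |
| REE | 12.10 | at least 3 h | no |
| 24 h blood pressure | 12.9 | none (workday) | no |
| EndoPAT (RHI) | 12.2 | none | no |
| Pulse wave analysis | 12.12 | none | no |
| FMD | 12.25 | none | no |

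**2. Do the visit windows fix it indirectly?** Visit 2 may fall on days 9 − 4 = 5 to 9 + 4 = 13 after Visit 1. Visit 4 may fall on days 28 − 7 = 21 to 28 + 7 = 35 after Visit 2. Under strict alternation, Visits 1 and 2 can therefore fall in the same phase or in opposite phases. Which phase either visit falls in cannot be derived, because Visit 1 has no phase and no ADF start day is given for the RCT.

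**3. Is it recorded?** The CRF takes dietary habits in general (9.3), and the food frequency questionnaire covers the past four weeks (12.8). Neither gives the state on the day. The glucose sensor is worn up to Visits 2 and 4 and might hint at the preceding day there, but no such use is planned. It is applied at Visit 1, so it cannot show the day before the Visit 1 OGTT. Under the section 11.1 table that is the only OGTT both cohort groups share.

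**4. How large could the effect be?** The protocol has no figure for this to reproduce, and none for the acute effect. The scale comes from section 12.26: HOMA-IR mean 3, SD 1.1, planning effect 15%, that is 0.15 × 3 = 0.45. Group sizes are the 30 and 60 of the synopsis, which carry the reduced total of 90; sections 10.1 and 12.26 still state 50 and 50.

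Two quantities are assumptions: p, the share of the ADF group tested after a fast day, and a, the acute relative shift in HOMA-IR (direction left open).

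- Shift in the ADF mean = p × a × 3.
- Standard error of the difference = 1.1 × √(1/30 + 1/60) = 0.246.
- Chance of a two-sided p<0.05 with no chronic effect: noncentral t, 88 degrees of freedom, noncentrality = shift / 0.246. The extra variance from mixing phases is ignored.

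With p = 0.5:

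| a | Shift | Share of 0.45 | Noncentrality | Chance of p<0.05 |
|---|---|---|---|---|
| 10% | 0.15 | 33% | 0.61 | 9% |
| 20% | 0.30 | 67% | 1.22 | 23% |
| 30% | 0.45 | 100% | 1.83 | 44% |

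With p = 0.25 the last column is 6, 9 and 15%. With p = 0 the shift is 0 and the rate is 5%.

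Section 12.26 says a multiplicity correction will be applied. With Bonferroni over the seven outcome bullets of section 8.1 (my choice of family, level 0.05/7), the p = 0.5 figures fall to about 2, 7 and 18%. The shift in the mean is unchanged by any correction.

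**The case against.** **The second OGTT.** The ADF-only OGTT at Visit 2 may well be meant to capture both states. That is a plausible reading, and it weakens any claim that the matter was overlooked. It does not settle it. The protocol does not state that purpose, ties neither OGTT to a phase and does not name the one used in the group comparison. Section 11.2 lists the test without the ADF restriction. It would also cover only the OGTT indices.

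**Length of the fast.** A reader might infer that ADF participants tested after a fast day have gone about 36 hours without food. The documents do not support this. The phrase "alternated with a 100% restriction" in section 5 describes animal models. The same paragraph says human versions often allow some food on the fast day, and the protocol never defines the regimen practised here. Someone who eats on the evening of a fast day may have the same overnight interval as a control. What stands is that the state is undefined.

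**Scope.** It would be too broad to say that all primary outcomes are affected. DXA fat mass and carotid IMT hardly respond to a single day, and multi-day glucose monitoring spans both kinds of day.

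**Size.** Taking 44% as the size of the problem would also go too far. It is the top of an assumed range, before a correction that the protocol promises, in analyses it calls descriptive and exploratory. The correction lowers the chance of a false claim but leaves the bias in the estimate.

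**Objective.** The short term in section 6 means the randomized ADF period, not a single fast day, and the design does separate it from long-term practice. The problem is that either contrast can carry an acute component.

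**Conclusion.** The point holds for the acutely sensitive outcomes: OGTT and fasting insulin indices, REE, RHI, FMD and augmentation index, appetite hormones and the single 24 h blood pressure recording. For these the protocol neither fixes nor records the phase of the ADF cycle, so a compliant study can mix an acute fast with the effect of ADF on one side of the comparison. For the Visit 1 OGTT, nothing the protocol collects would allow the two to be separated afterwards.

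The size is unknown. Under the stated assumptions the HOMA-IR bias ranges from one third of the planning effect to all of it. The logical gap does not depend on those values. It disappears if every ADF participant is in fact booked in the one phase that matches the controls, but the protocol does not require that. This should be corrected. It does not invalidate the study.

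**What to change.** 1. In sections 11.1 to 11.3 and 12.1, name one phase of the participant's own ADF cycle for every acutely sensitive measurement that enters a between-group comparison, and apply it at Visit 4 of the RCT. The morning after a feed day is one example, because it matches the controls' fast length.
2. State which of the two ADF-group OGTTs enters the group comparison, label the other as a within-ADF comparison, and reconcile the section 11.1 table with section 11.2. REE, EndoPAT, FMD and pulse wave analysis are scheduled at the same visit as the second OGTT and would take on its phase, so the text should say which phase Visit 2 has.
3. Specify the phase of the 24 h blood pressure recording separately in section 12.9. The device is applied at Visit 1. Under strict alternation, a Visit 1 that follows a feed day is itself a fast day, so the recording would fall mainly on a fast day.
4. Record date and time of last intake and fast/feed status at every visit.

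Cost: slightly less flexible appointments and one CRF item, with no added procedure. The windows allow it: if Visits 1 and 2 are to share a phase under strict alternation, gaps of 6, 8, 10 or 12 days are available. The workday condition for blood pressure narrows the choice somewhat further.
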